5.1 Study arms

Patients will be randomized in a 1:1 fashion using a random number generator (www.randomizer.org) to either 1 of 2 groups, CKM Jumpstart Tool or Usual Care. All enrolled patients will complete surveys within 2 weeks of their following clinic visit with their provider (T2), and about 3 months after this clinic visit (T3). All study procedures will be conducted either by phone or in-person, at the patient's convenience. Each visit will take about 20 minutes.

The CKM JumpStart Tool

The CKM JumpStart Tool is a 1-page handout that describes the values of a patient and words that a provider can try with the patient to explore the patient's values more and to provide a values-based introduction to CKM. The values describes in the CKM JumpStart Tool is based on a patient's response to a single validated question that asks the patient, if they had to choose, do they value care directed at longevity or comfort. A patient may also indicate whether they are unsure what kind of care they value more. Because there are 3 potential responses to the values question (longevity, comfort, unsure), there are 3 different versions of the CKM JumpStart Tool. (Appendix A.1 Intervention Materials: CKM JumpStart Tool Versions). The CKM JumpStart Tool does not contain any identifying information about the patient.

Patients who are randomized to receive the CKM Jumpstart Tool will be surveyed at T1. Using the patient's answer to the values question, study staff will generate a CKM JumpStart Tool prior to their upcoming clinic visit with their provider. Study staff will inform the patient that their response to the values question will be shared with their provider prior to their next clinic visit and that their providers might bring up their values and treatment options for kidney disease, if the

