5.6 Data Analysis

Feasibility and acceptability: As our primary outcome, and measure of feasibility, we will compare the proportion of patients in each study arm who reported having discussed CKM with their provider at T2 and T3. Based on prior work, the rate of patient-reported discussion of CKM with their health care providers in usual care settings is approximately 3%. The target sample size (n=76) is estimated to provide 80% power (two tailed, $\alpha=0.05$) to detect an absolute difference of 25% or more in rates of patient-provider discussion of CKM between the intervention and control groups assuming a 30% attrition rate. We will also evaluate the proportion of patients in each arm who has documentation in their nephrology clinic notes that CKM was discussed with the patient at T2 and T3.

As a measure of acceptability, we collect attrition rates at T2 and T3. We will further assess user experience of the CKM JumpStart by performing a qualitative analysis of post-intervention interviews with patients and providers, coding for themes elucidating pros, cons and other considerations with using the CKM JumpStart Tool and discussion about CKM.

Exploratory outcomes: We will assess change (i.e., T3-T1 and T2-T1) in decision conflict about treatment decisions for advanced CKD and quality of communication scores. We will also assess change in the proportion of patients who reported receiving goal concordant care at each study time point based on patients.

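### Does the sample of 76 patients fall short of its stated 80% power once 30% attrition is taken off?

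*Protocol*

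**What the plan says.** Section 5.6 (Data Analysis) defines the primary outcome as a between-arm comparison: "we will compare the proportion of patients in each study arm who reported having discussed CKM with their provider at T2 and T3". The planning rate comes from prior work: "the rate of patient-reported discussion of CKM with their health care providers in usual care settings is approximately 3" per cent. The power statement reads "The target sample size (n=76) is estimated to provide 80% power", two-tailed at 0.05, "to detect an absolute difference of 25% or more in rates of patient-provider discussion of CKM", "assuming a 30% attrition rate". Section 5.1 (Study arms) sets the allocation: "Patients will be randomized in a 1:1 fashion using a random number generator".

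The protocol names neither the test for the primary comparison nor the formula behind the 76. The SAP is not at hand.

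**The concern.** A 3% control rate with about 26 patients per arm is where approximations for two proportions disagree. The expected number of discussions in the control arm is 26.6 × 0.03 = 0.8, and the average over both arms is 26.6 × 0.155 = 4.1. A reader who checks the claim with the pooled formula, or who assumes Fisher's exact test because the counts are sparse, gets a figure clearly below 80%.

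The number 76 also lies near 58 × 1.3 = 75.4. That is what results from taking 29 per arm (the unpooled formula) and inflating by 1.3 instead of dividing by 0.7, so an attrition slip seems possible.

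If the power were overstated, a null result on the primary outcome would be read as stronger evidence against a 25-point effect than it is. The future trial that this pilot is meant to inform could then be planned on too small a detectable difference.

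**Working it through.** **Inputs.** From section 5.6: p₁ = 0.03; a difference of 0.25, read as p₂ = 0.28; two-sided α = 0.05 (z = 1.960); power 80% (z = 0.8416); attrition 30%; N = 76. From section 5.1: 1:1 allocation. Evaluable: 76 × 0.7 = 53.2, or 26.6 per arm. Assumption: attrition is equal in the two arms.

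**Step 1: reproduce the 76 and the 80%.** Arcsine formula (Cohen's h):

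- h = 2·asin(√0.28) − 2·asin(√0.03) = 1.1152 − 0.3482 = 0.767
- n per arm = 2 × ((1.960 + 0.8416)/0.767)² = 26.68
- total evaluable = 53.36; enrolled = 53.36/(1 − 0.30) = 76.2
- power at 26.6 per arm = Φ(0.767 × √(26.6/2) − 1.960) = Φ(0.837) = 79.9%

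Both stated figures come out, with attrition handled correctly by division. The arcsine result (76.2) is also closer to 76 than the multiply-by-1.3 route (75.4). Nothing in the protocol points to the latter.

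**Step 2: other planning formulas at the same inputs.** The mean rate is 0.155.

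| Formula | n per arm for 80% | Power at 26 / 26.6 / 27 per arm |
|---|---|---|
| Arcsine | 26.68 | 79.0% / 79.9% / 80.5% |
| Unpooled variance | 28.97 | 75.6% / 76.6% / 77.2% |
| Pooled variance | 31.7, rounded up to 32 | 71.4% / 72.4% / 73.1% |

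By the pooled formula, 80% would need 64 evaluable, or 64/0.7 = 91.4, so 92 enrolled.

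**Step 3: exact power, with no planning approximation.** The binomial probabilities were summed over every table that the test rejects, at 3% versus 28%:

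| Control / intervention | Uncorrected chi-square | Its maximum true error over all common rates | Fisher's exact |
|---|---|---|---|
| 26 / 26 | 79.1% | 5.6% | 62.3% |
| 26 / 27 | 81.0% | 5.5% | 59.9% |
| 27 / 26 | 78.4% | 5.5% | 69.3% |
| 27 / 27 | 80.9% | 5.7% | 59.2% |

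At a common rate of 3%, the chi-square test's true error is about 0.7%. Its peak of 5.5–5.7% occurs at common rates of about 14–20% (and, by symmetry, 80–86%).

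Boschloo-type unconditional exact tests give 70.0–78.4%. The best monotone test that holds each tail at 2.5% for every common rate reaches 76.1–78.4%. If only the total error is held at 5%, a test with about 86% power exists, though at low rates it is in effect one-sided.

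**Reading.** The exact power of the uncorrected chi-square brackets 80%, and the arcsine formula lands inside that range. Here the pooled formula understates what that test delivers: 72.4% against 78.4–81.0%.

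**The case for a change.** The strongest case against the figure is that reproducing it is not the same as its being sound. If the arcsine statistic itself were used as the test, its true type I error would be about 17% at a 3% common rate, so the formula that yields 76 is weak ground at this rate and size. Fisher's exact test is a common choice for counts this sparse, and with it the chance of missing a 25-point effect is 31–41%, not 20%. Under strict control of each tail at every common rate, no test reaches 80%. By the pooled formula, the difference detectable with 80% power is about 28.5 points.

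The numbers stand; the inference does not. The arcsine formula matters here as a planning approximation, and as such it agrees with the exact power of the chi-square test; nothing in the protocol says the arcsine statistic will be the test. The strict criterion excludes the chi-square test for an excess of at most 0.7 points, at common rates far from the planning rate. Many statisticians would accept that. Even under the strict criterion, the best test comes within 2 points of 80% for one of the four splits (78.4%), against a figure given as an estimate and built on an approximate 3%.

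A control rate above 3% would also lower power: by the pooled formula, a 25-point difference has 68% at an assumed 5% and 59% at an assumed 10%. These rates are assumptions from outside the protocol. They show sensitivity to the planning rate, not an error in the calculation.

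**Conclusion.** The concern does not hold. The stated 80% power with 76 enrolled follows from the protocol's own inputs: 76.2 enrolled and 79.9% power by the arcsine formula. A common analysis, the uncorrected chi-square test, delivers 78.4–81.0% exact power at 26–27 per arm. Attrition is correctly accounted for.

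The lower figures, 72% by the pooled formula and 59–69% by Fisher's test, are right for those methods. They become the study's power only if one of those methods is chosen, and the choice of test is commonly left to the SAP. Preferring one accepted method to another does not make the stated number wrong.

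This rests on three assumptions: 3% versus 28% is the intended contrast, attrition is equal between arms, and a worst-case true error of up to 5.7% is acceptable for a nominal 5% test in a pilot. If the SAP names Fisher's exact test, the 80% will not apply to that analysis.

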5.5 Study Evaluations

Patients

The date of study enrollment will be the date that a patient's consent is obtained. Patients will be followed through patient's death, date of study withdrawal, or study completion, whichever is earliest.

Patients will complete the following surveys and interviews at enrollment (T1), within 2 weeks of their following clinic visit with their provider (T2), and about 3 months after this clinic visit (T3). All study procedures will be conducted by phone. Each phone call will take a total of 15 to 30 minutes. We will give participants a \$20 gift card for each study visit that they complete. Gift cards will be mailed within five business days of a completed call.

Demographic survey (Appendix C.1): At T1, patients will be asked their gender, age, race, prior education, total annual household income, current employment status, and self-rated overall health.

EuroQol 5D (Appendix C.2): At T1, patients will be asked to complete a 5-item survey inquiring different domains of quality of life, including mobility, self-care, usual activities, pain/discomfort, and anxiety/depression, on a 5-point scale.²⁴

Control Preferences Scale (Appendix C.3): At T1, using a single question, patients will be asked to rate on a 5-point scale their preference in taking lead in medical decision-making.

Healthcare values (Appendix C.4): At T1, using a single validated question, we will ask patients about their preference for either extending life or preserving comfort. Patients will also have the option of indicating that they are uncertain about which they prefer. We will also ask whether they perceive that their provider provides care that is mostly directed at extending life or preserving comfort or are unsure. Patients will be considered as receiving goal concordant care if they perceive the care that they receive matches the care that they value.

Quality of communication (Appendix C.5): At T1, T2 and T3, patients will be asked to rate the quality of serious illness communication with their providers using the 13-item subscale of the Quality of Communication Questionnaire.²⁵⁻²⁷

Discussion of treatment options (Appendix C.6): At T1, patients will be asked if they had ever discussed CKM and dialysis with their provider. At T2 and T3, patients will again be asked if they had discussed these topics since the last study visit.

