Decisional conflict (Appendix C.7): At T1, T2 and T3, patients will be asked to complete the 4-item SURE Test to assess their preference for dialysis vs. CKM and the decisional conflict they have about their options.^{28,29}

Post-clinic patient interview (Appendix C.8): At T2, patients assigned to the intervention will be invited to answer 4 open-ended questions about their clinical encounter with their provider. Questions will pertain to topics discussed during the encounter with their clinician, whether their provider asked them about their values, whether CKM was discussed, and their perception of CKM based on the conversation. Interviews will be audio-recorded then transcribed. We estimate that an interview will take 10-15 minutes to complete.

Documentation of discussion of CKM with patients: At T2 and T3, we will review each patient's recent nephrology clinic notes to determine whether providers documented a discussion with patients about CKM. Documentation will be transcribed into a Word document without personal identifiers.

Providers

Demographic information: From publicly available directories, we will ascertain providers' gender, race, and years since completing their medical degree.

Use of the CKM Jumpstart Tool (part of Appendix B.3): For providers whose patients were assigned to the intervention, we will ask them after their visit with their enrolled patient (T2) whether they had used the CKM Jumpstart Tool during their visit, and if not their reasons for not using the Tool.

Post-clinic provider interview (Appendix C.9): For providers who used the CKM Jumpstart Tool, we will ask 4 open-ended questions about their clinical encounter with the patient and their experience using the CKM JumpStart Tool. Clinician responses will be recorded in writing, then transcribed into a Word document. We estimate that an interview will take 5 minutes to complete. Interviews will be conducted by phone or in-person in a private clinic room or office of the provider, per the provider's preference. Providers will be offered a \$10 gift card for their participation.

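### Change in goal-concordant care is planned at every time point (section 5.6), but section 5.5 schedules the questions behind it at T1 only

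*Protocol*

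**What the plan says.** Section 5.6 of the protocol, under exploratory outcomes, says the team will "assess change in the proportion of patients who reported receiving goal concordant care at each study time point based on patients". The sentence stops there without completing its thought, so it names no data source.

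The source is in section 5.5. Its Healthcare values paragraph opens "Healthcare values (Appendix C.4): At T1, using a single validated question, we will ask patients about their preference", goes on to say "We will also ask whether they perceive that their provider provides care that is mostly directed at extending life" (or comfort, or unsure), and ends with the definition: "Patients will be considered as receiving goal concordant care if they perceive the care that they receive matches the care that they value". The only visit named in that paragraph is T1.

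Other instruments in the same section have their repeats written out:
- "Quality of communication (Appendix C.5): At T1, T2 and T3, patients will be asked to rate the quality"
- "Decisional conflict (Appendix C.7): At T1, T2 and T3, patients will be asked to complete the 4-item SURE Test"
- for discussion of treatment options (C.6), after a T1 question, "At T2 and T3, patients will again be asked if they had discussed these topics since the last study visit"

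Goal-concordant care is also named as a preliminary outcome in section 3.0 (Objectives) and section 5.0 (Study Design). The Abstract plans to explore it between arms.

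**The concern.** A change needs at least two measurements. Section 5.6 needs goal concordance at T1 and again after the clinic visit, whereas section 5.5 as labelled provides it once, before the intervention has happened.

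If the surveys are run to the section 5.5 labels, the pilot will hold no post-visit information on one of its two named preliminary outcomes. The comparison of arms promised in the Abstract could then be made only at T1, where any difference reflects chance and not the Tool. The loss would be permanent, because an analysis plan can choose a method but cannot create answers that were not collected.

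**Working it through.** The protocol gives no figure to reproduce here. The check sets the collection schedule in section 5.5 against the analyses in section 5.6.

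**Step 1. Outcomes that section 5.6 analyses as change**

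| Outcome | Instrument | Visits labelled in 5.5 |
|---|---|---|
| Decisional conflict | C.7 | T1, T2, T3 (3 of 3) |
| Quality of communication | C.5 | T1, T2, T3 (3 of 3) |
| Goal-concordant care | C.4 | T1 (1 of 3) |

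Two of the three have the schedule their analysis needs.

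**Step 2. Does the lead-in to section 5.5 supply T2 and T3?** It names all three visits for the whole list of surveys and interviews. But the list includes items labelled for T1 alone, for example "EuroQol 5D (Appendix C.2): At T1, patients will be asked to complete a 5-item survey", as well as the demographic survey and the Control Preferences Scale. It also includes a post-clinic interview held at T2 alone. The lead-in therefore cannot fix any one instrument's schedule. The item labels do that, and C.4 carries the same bare T1 label as the baseline-only items.

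**Step 3. Is there another source?**
- The T2 patient interview (C.8) is open-ended and offered to the intervention arm only. It covers whether the provider asked about values, not which kind of care the patient values or perceives.
- Section 5.1 mentions the values question only in the T1 survey. It says surveys are completed at T2 and T3 without listing which.
- Nothing else in the protocol describes a later measurement.

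**Step 4. What can be computed.** With three visits there are two changes from T1: T2-T1 and T3-T1.

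| Reading of section 5.5 | Changes computable |
|---|---|
| Both C.4 questions at T1 only | 0 of 2 |
| Perceived care repeated, preference carried forward from T1 | 2 of 2 |
| Both questions repeated | 2 of 2 |

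The second and third rows measure different things. One compares later care with the preference held before the visit; the other compares it with the preference held at the time. Section 5.5 does not say which is meant.

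**Step 5. Ceiling on the data affected.** 76 patients x 2 post-T1 visits = 152 patient-visits with no C.4 label, at full enrolment and no attrition. If the 30% attrition assumed in section 5.6 applied at both visits, this would be 152 x 0.70, or about 106. These are counts of contacts, not measures of bias or precision.

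**The case against.** The best counter-argument is that this is a missing label and not a missing measurement. Section 5.6 refers to every time point, the lead-in to section 5.5 names T1 to T3, and the Abstract plans a between-arm comparison that would be pointless without post-visit data. Read as a whole, the protocol seems to intend repetition. In addition, the T1 label is attached grammatically to the preference question. The perceived-care sentence has no label, and the definition does not demand that values be asked again, so repeating perceived care alone would give a usable change. Appendix C.4 and the structured data forms are not shown and may settle the matter. The outcome is exploratory, in a feasibility pilot.

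Much of this stands. A repeat may well be intended, and the T1-only reading is the natural one but not the only one. Section 5.1 is close to neutral, since the Tool can only be built from a pre-visit answer whether or not the question is repeated later. The inconsistency is better seen as a drafting conflict than as a deliberate T1-only design.

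None of it makes the two sections agree. Section 5.5 writes out repeats for C.5, C.6 and C.7 and omits them for C.4. That section 5.6 implies later collection is itself the conflict. If perceived care alone is to be repeated, the protocol has to say so.

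**Conclusion.** The concern holds. Sections 5.5 and 5.6 contradict each other on goal-concordant care: the analysis needs post-visit answers that the schedule does not provide. On the natural reading, 0 of 2 planned changes can be computed for one of the two preliminary outcomes named in the Objectives and Study Design.

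This rests on the visible text, in particular on taking the T1 label as governing the whole Healthcare values paragraph. Confidence in that reading is medium, because of the unlabelled perceived-care sentence and the unseen appendix. The contradiction in the text does not depend on which reading was intended.

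The reach is limited. The primary outcome, chart documentation, decisional conflict and quality of communication all have clear schedules. It should be fixed because the data cannot be recovered afterwards and the correction costs almost nothing.

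**What to change.** In section 5.5, state that both C.4 questions, valued care and perceived care, are asked at T1, T2 and T3. Complete the unfinished sentence in section 5.6 so that it names C.4 as the source. The cost is 2 questions x 2 visits = 4 extra answers per patient, at contacts already scheduled, plus the text edits. No extra visits or patients are needed.

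If only perceived care is to be repeated, section 5.5 should say so and state that concordance at T2 and T3 is judged against the T1 preference.

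If neither question is to be repeated, delete the goal-concordance change analysis from section 5.6 and the between-arm aim from the Abstract. In sections 3.0 and 5.0, remove goal-concordant care as a preliminary outcome or describe it as baseline only. This fallback gives up a stated aim, so the first option is preferable.

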5.7 Withdrawal of Subjects

Subjects will be informed during the consent process and at each study visit that they can choose to withdraw from the study at any point in time.

There are no anticipated circumstances under which subjects will be withdrawn from the research without their consent. There are no anticipated consequences of a subject's decision to withdraw from the research. During data collection, study interviewers will assure participants that they can, at any time during the interview, refuse to answer any questions asked of them and may at any time elect to withdraw from the study. If a participant elects to withdraw during the phone call, the interviewer will immediately end the interview or questionnaires.

5.0 Reporting

We do not anticipate any adverse events that might occur. However, any and all unanticipated problems, serious adverse events and protocol deviations will be recorded and reported immediately to the study Principal Investigator. Any serious adverse events and/or serious problems will be reported to the IRB within 5 business days. Additionally, the ISO and Privacy Officer will be notified within one hour of any improper use or disclosure of study data. The Principal Investigator will be the monitoring entity responsible for ensuring that all measures related to data security and protection of subject privacy and confidentiality are being followed.

Subjects will be informed to contact the PI for all urgent and non-urgent questions and concerns at the following: [name], [contact].

6.0 Privacy and Confidentiality

The proposed work will use protected health information. All study personnel who will have access to protected health information and/or will be involved in obtaining subject consent will be required to complete all necessary training in the protection of human subjects and privacy

through the Department of Veterans Affairs (VA) Learning University Talent Management System (TMS). All study personnel who have access to study and patient data have been approved by both the UW and VAPS.

All subjects will be given a unique study ID, and data collected for this study will be associated with study IDs only. A separate crosswalk file linking study IDs with personal identifiers will be kept separate from data analysis files. Data analysis files will not contain personal identifiers. Chart passages containing information about discussion of CKM will be transcribed without personal identifiers. All interviews will be transcribed and purged of any personal identifiers by the transcriptionist. Data analysis will be conducted using only the de-identified transcripts. Patient responses during interviews will also be kept confidential from their providers and close persons. Likewise, information shared by close persons will not be shared with patients.

Study data will be aggregated for presentations or publications related to the study in order to conceal the identities of subjects.

